See letter of support from consultant, [name], Director of the HCC Biostatistics Shared Resource. Sample size justification: Eighty participants (40 per group) will be enrolled. A sample size of 40 will allow us to establish estimates of abstinence with 95% confidence intervals (CI) for each arm, and to assess the precision in our estimates. The goal is to establish reasonably precise effect sizes to power a future study so we do not expect to achieve statistical significance in group comparisons. 95% CI and corresponding half widths for exemplar abstinence rates are provided in Table 2. With 40 patients per arm and an observed abstinence rate of 0.30, we can be 95% confident that the true abstinence rate is between 0.17 and 0.47 for that intervention.

Statistical Analysis: Aims 1 and 2 will be achieved by estimating abstinence rates with exact 95% CIs. Differences in rates and the 95% CIs for the differences will also be estimated. Baseline clinical and demographic variables will be assessed with summary statistics and reported by group, and compared to evaluate balance across groups. While the main aim of this pilot trial is to establish effect size estimates, we will also conduct a preliminary examination of between group differences in abstinence using logistic regression. With respect to exploratory analyses, logistic regression will also be implemented to evaluate effects of mediators and moderators of treatment on abstinence, and linear regression will be used to compare costs in the two arms. Given the pilot nature of this study, emphasis is on estimating effect sizes and variances and not statistical significance of associations. A sample size of 40 patients per group should provide sufficient preliminary data to guide me in my future research in this area.

Table 2. Example Effect Size Estimates

Observed Rate of Abstinence	95% CI	Half Width
0.50	(0.34,0.66)	0.16
0.30	(0.17,0.47)	0.15
0.10	(0.03,0.24)	0.10

C4. Recruitment, Feasibility, and Timeline

Patients eligible for this study will come from the LCS programs at HCC Downtown, Mount Pleasant, North Charleston, West Ashley, Lancaster, Chester, Florence, and Columbia. [name] is the Co-Director of program, and I will have full access to all LCS patients who smoke. To date, the program has screened more than 300 patients and is expanding outreach efforts. Between 11/1/16 and 2/1/17, 21 current smokers were screened (7 per month). Not all patients may be interested in participating in a research study, so I conservatively estimate that I could recruit 2 current smokers per month. The LCS program is in the midst of launching a \$30,000 ad campaign, and the nurse practitioner dedicated to the program is visiting primary care practices every week. Thus, due to these ongoing outreach activities, the program projects screening at least 20 current smokers per month over the next 6 months, and I do not anticipate a problem with recruitment. The study timeline is presented in Table 3.

Table 3. Study Timeline

Months 1-12:	IRB approval, create texting materials
Months 13-17:	Test the text protocol; obtain medication, train staff
Months 18-49:	Recruit 80 participants and follow for 3 months
Months 50-60:	Follow-up, data analyses, prepare presentations and publications.

D. Summary and Future Directions

The proposed independent research extends the rigorous research methods found in recent studies of NRT and gain-framed text messaging interventions in the general population to the important, yet understudied clinical population of LCS patients. The proposed research has numerous strengths including: a) a timely research question, namely how to optimally enhance smoking cessation in current smokers who are receiving LCS; b) gain-framed smoking cessation text messaging specifically developed for LCS patients; c) a robust pharmacotherapy strategy ; d) a rigorous study design and analyses to establish effect sizes for future research in this area, and e) potential to easily translate the findings to the growing number of LCS programs across the country. Research on tobacco treatment interventions for LCS patients could reduce the future incidence of cancer and mortality for this high-risk patient population. This is an area of research where creative and rigorous research is desperately needed to capitalize on the teachable moment of LCS and extend effective tobacco treatments. Further, this project will allow me to extend my training goals of health services research to an avenue of research. My career development plan and independent research proposed herein will ensure that I am fully capable of achieving my long-term career goal of contributing to the research on tobacco treatment in an oncology setting, and LCS more specifically.

PROTECTION OF HUMAN SUBJECTS

RISKS TO THE SUBJECTS

Human Subjects Involvement and Characteristics

In this experiment, participants will be recruited to participate in a smoking cessation study in the context of lung cancer screening. For the study, we will use the following inclusion and exclusion criteria. Inclusion: 1) 50 years or older (we see no reason for upper limit given supportive evidence for cessation among elderly), 2) 20 pack year history of smoking (i.e., the base population of high risk smokers to get screened), 3) current smoker (defined as self report any smoking in the past 7 days), 4) willing to be randomized, 5) English speaking; 6) access to device(s) that allows for text messaging and downloading apps; Exclusion: 1) unstable psychiatric/medical conditions such as suicidal ideation, acute psychosis, severe alcohol dependence, or dementia, 2) in the immediate (within 2 weeks) post myocardial infarction period, 3) serious arrhythmias, 4) unstable angina pectoris, or 5) hemodynamically or electrically unstable, or 6) currently taking part in any other tobacco treatment program or using cessation medication (i.e., taking NRT or other cessation medications, enrolled in the Quitline, in another drug study). We intend to enroll 80 participants.

Sources of Materials. The sources of data for participants in this project is open-ended questions through interviewer-administered self-report questionnaires of background, behavior (eg, smoking), and cognitions (eg, motivation). Questionnaires will be administered at the time of intake, at the end of the 8-week intervention period, and at the 3-month follow-up. All responses will be collected on a secure, password-protected, electronic Web-based form, or on paper forms if the participant does not have access to the internet. The data will be sent or entered into a secure database in REDCap. Only research staff have access to the database.

Potential Risks. The risks associated with participating in these studies are minimal. Participants are informed in advance about the content of the educational materials that they will receive and the kinds of questions that

they will be asked. They are also informed that they may terminate participation without penalty. Moreover, they are informed that, if any pre- or post-intervention question seems too personal or if they prefer not to respond for any reason, they can skip the question without penalty. Participants in the treatment arm will be offered nicotine replacement therapy (NRT), and there are risks in taking NRT. The NRT used in this study (patch and lozenge) is a standard smoking cessation intervention and is available over-the-counter. The most common adverse effect of nicotine transdermal delivery is topical skin irritation, ranging from mild erythema to a more generalized skin reaction, frequently in subjects with a history of eczematous dermatitis. The most common adverse effects of nicotine replacement lozenges are upset stomach and heartburn.

ADEQUACY OF PROTECTION AGAINST RISKS

Recruitment and Informed Consent

Participants will be recruited through the lung cancer screening programs at Medical University of South Carolina/Hollings Cancer Center Downtown, Mount Pleasant, North Charleston, Lancaster, Chester, Florence, and Columbia. Informed consent will be obtained prior to beginning the study.

Protection Against Risk. We will take the following steps to reduce the direct risk of participating in the study:

- (a) If offended in any way, participants can terminate any part of participation without penalty. In all of the preliminary experiments reported in this proposal, no participant reported being unduly distressed or upset about his or her participation, although occasionally participants do drop out because they are no longer interested in the study or because it is taking too long and they have other obligations. To date, no one has expressed significant regret about having participated.
- (b) If a participant or potential participant appears extremely distraught or clearly preoccupied, investigators will use their discretion as to whether or not to attempt to enroll the individual into the study or suggest that their participation stop.
- (c) If a participant reports an adverse effect of the NRT, we will work with them to ensure that they are using the medication properly. If it is determined that they have been using the medication properly and are still experiencing an adverse effect, they will be encouraged to discontinue use of the NRT.
- (d) Several steps will be taken to safeguard the confidentiality of subjects and their data. All research data that is collected will be assigned a study participant number and that number will only identify participants in digital databases. The names of participants will not be associated with this data and assessments will be maintained according to participant study number. A master list connecting participant study numbers to participant names will be kept in a locked file cabinet where it can only be accessed by senior level project staff. Any information published as a result of the study will be such that it will not permit identification of any participant. Right to privacy for participation in this research will be protected through coding of data and proper storage of research records. Consistent with mandated reporting requirements for health providers, we advise participants that in the case of child abuse or neglect, threat of injury to self or others, or intention to destroy property, that we may need to intervene and report that information to the proper authorities. Subjects will be informed of this limit to confidentiality as it is stated in the informed consent document. The PI and the research staff will have access to PHI. Organizations that have a responsibility for protecting human participants, including the MUSC IRB, may have access to subjects' medical records containing PHI. Additionally, the funding agency (National Cancer Institute) may have access to subjects' medical records containing PHI.

POTENTIAL BENEFITS OF THE PROPOSED RESEARCH TO THE SUBJECTS AND OTHERS

Participants will receive advice about quitting smoking. Subjects participating in this study may benefit from the information provided to them by the counselor by having their motivation to quit smoking bolstered and by receiving advice that helps them to quit smoking. Although the investigators cannot know for sure whether this

study will be of any direct benefit to participants, the results of the study will facilitate the development of more effective smoking cessation intervention materials, which will promote tobacco and cancer control.

IMPORTANTCE OF THE KNOWLEDGE TO BE GAINED

Although the proposed research poses minimal risks to participants, it has high potential for advancing knowledge in the field of smoking cessation. The proposed research will augment current knowledge on the efficacy of interventions administered in the context of lung cancer screening. Administering a sample of NRT and gain-framed text messages may help to identify a low-cost method for increasing the effectiveness of a moderate-intensity intervention for smoking cessation that has the potential to reach smokers at high risk of lung cancer, thereby bolstering tobacco and cancer control efforts across the United States. Given the minimal risks in the study and the potentially great benefit to science, the risk/benefit ratio in this study appears quite favorable.

DATA AND SAFETY MONITORING PLAN

Monitoring for data integrity and safety will be the responsibility of the investigators, and the MUSC Institutional Review Board (IRB).

Data Monitoring. For this review process, I will compile a semiannual report of aggregate data that contains screening data, baseline demographics, retention data, adverse events data, accrual status including projections, times to milestones, and any other data that will help in the assessment of the experiments and discuss the report with my full mentoring committee. Based on this report, each mentor will make 1 of 2 recommendations: 1) maintain the current study protocol; 2) schedule formal meeting immediately with the MUSC IRB. If any committee member recommends a meeting, this will be scheduled within 1 week. The committee will vote on whether the current study should: 1) continue recruitment unchanged; 2) continue with a protocol amendment; 3) stop the study pending further investigation. If after this meeting any committee member votes to request a protocol modification, the MUSC IRB will be immediately informed by [name].

Safety Monitoring. This protocol presents minimal risks to participants. The study involves receiving gain-framed text messages and NRT, and to complete follow-up interviews. The only risks that can be anticipated from this study is loss of confidentiality, and this will be protected using the procedures described in the "Sources of Materials" section above. In addition, participants may experience side effects from NRT (as previously described). Nonetheless, because we anticipate that behavior change (which will pose minimal risk to participants) will be a product of participating, we have developed a safety monitoring plan to report adverse events resulting from behavioral changes.

Monitoring to identify adverse events. Prior to implementing the randomized study, research staff will be trained to identify adverse events. Research staff will be instructed to provide [name] with a detailed description of the event. [name] will grade the event in conjunction with [name] within 24 hours. The following additional individuals will be informed immediately of serious adverse events: (a) the mentoring committee; (b) the National Cancer Institute (NCI); and (c) the MUSC IRB. All of these individuals and committees will receive a copy of a SAE Form within 48 hours, at which point a decision will be made whether to convene a meeting.

Plan for grading adverse events. Serious Adverse Events (SAE). The FDA's definition of serious adverse events (21 CFR 312) will be used. Serious Adverse Events include any untoward medical occurrence that at any dose results in death or the immediate risk of death, hospitalization or the prolonging of an existing hospitalization, persistent or significant disability/incapacity or a congenital anomaly/birth defect, new cancer, or medication overdose. Adverse events will be defined and graded for risk as follows:

Coding of Severity:

0 = No adverse event or within normal limits

1 = Mild adverse event

2 = Moderate adverse event

3 = Severe, resulting in psychiatric or medical hospitalization

4 = Life-threatening adverse event

5 = Fatal adverse event

Coding of Attribution will be made for adverse events grade 3 and above (ie, serious adverse events):

1 = Unrelated to study interventions

2 = Unlikely relationship to study interventions

3 = Possible relationship to study interventions

4 = Probable relationship to study interventions

5 = Definite relationship to study interventions

Plans for reporting serious unanticipated and anticipated adverse events. Serious adverse events, whether unanticipated or anticipated, will be reported immediately (within 24 hours) to the MUSC IRB and the National Cancer Institute, and a written report will be submitted within 48 hours. The PI and mentoring committee will evaluate the adverse event and determine whether the adverse event affects the Risk/Benefit ratio of the study and whether modifications to the protocol or the consent procedures are required.

Plans for reviewing and reporting nonserious anticipated or unanticipated adverse events. Any participants' experiences of anticipated and unanticipated adverse events will be reported on an annual basis to the MUSC IRB and the NCI as part of an annual progress report (NCI) and annual re-approval (MUSC IRB).

References

14. [name] B, Martino S, Latimer A, et al. Randomized trial: Quitline specialist training in gain-framed vs standard care messages for smoking cessation. *Journal of the National Cancer Institute (JNCI)* 2010;102:96-106; PMID: 20056957; PMCID: PMC2808347.
15. [name] B, O'Malley S, Katulak N, et al. Comparing gain- and loss-framed messages for smoking cessation with bupropion: A randomized controlled trial. *Psychology of Addictive Behaviors* 2007;21:534-44; PMID: 18072836; PMCID: PMC2527727.

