Aim 1: Conduct a 2-arm pilot randomized clinical trial with patients referred for LCS who smoke (N = 80) to evaluate 7-day point prevalence abstinence rates and determine effect size estimates among participants who receive a standard intervention (single, brief counseling session at time of LCS) versus an enhanced medication and text messaging intervention (MTI; standard intervention + 8 weeks NRT + gain-framed messages with medication use reminders).

Hypothesis 1.1: Compared to the standard intervention, NRT and gain-framed text messaging will produce higher rates of smoking cessation at the end of Week 8.

Secondary Aim 2: To develop effect size estimates for rates of smoking cessation at the 3-month follow-up.

Hypothesis 2.1: Compared to the standard intervention, NRT and text messaging will produce higher rates of smoking cessation at the 3-month follow-up.

Exploratory Aim 3: To examine mediators and moderators of smoking cessation outcomes (i.e., nicotine dependence, medication adherence, positive lung finding from the scan [e.g., nodule is present]).

Hypothesis 3.1: Patients with greater nicotine dependence will have lower rates of cessation compared to those who have less nicotine dependence. Those who are more adherent with medication regimens in general (as assessed at baseline), as well as those who are adherent with the NRT regimen throughout the intervention, will have higher rates of cessation compared to those who are less adherent. Patients with a positive lung nodule finding after LDCT will be more likely to quit smoking than those who have a normal LDCT scan.

Exploratory Aim 4: To conduct exploratory analyses of cost-effectiveness of the intervention.

Hypothesis 4.1: I expect that the treatment intervention will be more cost-effective than standard counseling alone.

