A2. Nicotine Replacement Therapy (NRT). NRT is an evidence-based pharmacological intervention for smoking that is easy for tobacco treatment providers to disseminate at the point of care because no prescription is required. Providing NRT is particularly useful because it can be delivered at LCS, does not require a prescription, and can increase the number of quit attempts and quitting.^{32,33} Uptake of cessation treatment is higher when accessibility is increased,³⁴ as would be the case when NRT is proactively provided at the point of LCS. [name] recently funded NCI R01 (Co-Is: [name], [name], [name]) will evaluate NRT sampling (a 2-week supply of dual NRT and suggestion to "try" the two medications) in a LCS population. I will be able to leverage the resources from that grant to assist with the conduct of this proposed study. The present study will differ from [name] R01 in that I will evaluate an 8-week dual NRT regimen. The first 2-week supply will be delivered at the point of screening in the treatment arm, and I will mail the 3 remaining 2-week supplies of NRT to the participant. This will further increase accessibility, reduce possible waste from non-use, and also reduce participant burden from picking up the medication (similar to a state smokers' quitline model). I will also assess medication adherence through the use of text messages (described below in A3) throughout the 8-week treatment period, and send novel text messaging reminders to use the NRT to enhance adherence.

A3. Text Messaging: Texting is a relatively low-cost way to reach smokers frequently and in the context of their day-to-day lives. Recent evidence shows that smoking cessation behavioral support programs provided by text message are effective.³⁵ Evidence from the texting literature also suggests that the framing of the text message may have an influence on behavior. Prospect theory³⁶ suggests that decision-making under conditions of risk is influenced by the way messages are delivered, or framed. The framing implications of

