If an eligible patient from MUSC Lancaster, MUSC Chester, MUSC Florence, or MUSC Columbia is interested in enrolling into the study, all study procedures will take place remotely. It is not feasible to perform study procedures in person due to the far distance from study staff, who are located at MUSC Charleston. Recruitment and all study procedures will follow the same procedures as described for MUSC Charleston sites, apart from using in-person methods. If the electronic medical record identified the patient as a smoker, or if the patient reports being a smoker at the time of their scan, the nurse practitioner will speak with the patient regarding the study and/or the patient will speak by phone with one of our study research assistants. The nurse practitioner will be given study flyers to hand out to eligible patients. Patients who express interest in the study will set up a virtual intake appointment with a research staff member. All participants recruited through these sites will complete the consent and baseline session using either 1) REDCap electronic consent (e-consent) combined with a phone discussion, 2) by mail combined with a phone discussion, or 3) a combination of these options.

All participants will have a smoking cessation counseling session with the lung screening nurse practitioner as part of standard clinical care. Of note, the treatment provided to study participants by the smoking cessation counselor in this study is a reimbursable service. This is important for 2 reasons: 1) NCI grant funds are not needed to support these high-cost services provided in this project, and 2) this increases the future translational possibilities of the intervention, as these methods will be sustainable at other cancer centers because insurance reimbursement will pay for these services. The counseling provided by the nurse practitioner will be based on practical counseling, which is a cognitive-behavioral, evidence-based, smoking cessation treatment modality.⁵⁵ The counseling session will last approximately 30 minutes, and all participants will be encouraged to set a quit date.

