NRT. In addition to the standard counseling described above, participants in the MTI arm will receive dual NRT (nicotine patch plus lozenge). An initial 2-week supply of 21 mg patches and 4 mg lozenges will be provided at the time of counseling or will be mailed to the participant within a week of randomization, and 3 additional 2-week supplies will be mailed out over the course of the subsequent 8 weeks. This mail-out model will allow us to assess participant use of the medications because participants will be contacted and asked how much NRT they used and if they would like to receive the next 2-week dose. Detailed information on each product, including instructions for use, will be provided in the take-home packet or emailed to the participant. We will inform patients about both single NRT use, as well as combined use, and participants will be given the opportunity to use the medications individually or together (participant choice, including none at all). Both patch and lozenge will be provided for four reasons. First, a number of studies demonstrate their efficacy when used singularly.⁵⁶ Second, they are both over the counter, increasing their utility within LCS settings where eligibility is minimal and instructions on use require nominal discussion. Third, whereas the patch provides a steady dose of nicotine throughout the day, the lozenge is used ad libitum and provides acute nicotine administration. These two mechanisms might appeal to smokers differently. Fourth, the majority of studies⁵⁷⁻⁶⁰ have shown that combined use of patch + lozenge is superior over placebo and single NRT products. Finally, the National Comprehensive Cancer Network Smoking Cessation Guidelines list combination NRT as first line pharmacotherapy. Those in the SC condition will receive standard counseling but no medications, and we will contact them every 2 weeks to inquire about use of any pharmacotherapies that they purchased on their own. At the time of patient contact regarding medications, research assistants will also assess point prevalence abstinence.

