***Use of Pharmacotherapies:** We will determine the amount and frequency of NRT used (per product), and will also determine use of products we provide vs. purchase of additional products. For all participants, at each refill or contact point during the 8-week time frame, we will ask how many total patches and lozenges were used since the last contact, and how many were used each day. I will also incorporate a text-message based medication use assessment, as previously described. This novel approach will allow us to collect a daily medication diary from each participant, instead of relying on retrospective report. After calculating a percentage of medications taken, medication adherence will be assessed as a mediator of treatment outcomes.^{70,71}

Attitudes Towards NRT: Attitudes towards NRT may differ depending on the amount of NRT they elect to receive, the types of NRT selected, and the patient experience with the medication. We will assess 1) positive, and 2) negative attitudes towards NRT, as well as 3) general knowledge of NRT.^{32,72-76}

Motivation and Confidence to Quit: We will assess motivation and confidence to quit smoking using our modification of the Contemplation Ladder^{77,78} which assesses readiness to quit in the next month.

*Findings from screening: Lung screening findings will be defined as pulmonary findings (nodule, cancer, emphysema, enlarged lymph nodes) and coronary findings (calcification).

Adverse Events: We will assess adverse events at each NRT refill time point for the MTI group. For the SC group, we will ask about adverse events at each contact point after LCS. We will grade and report the severity of adverse events as described in Protection of Human Subjects. Participants who have significant side effects from NRT use will be encouraged to discontinue NRT use immediately.

Texting Satisfaction Survey: We will assess participant satisfaction with the texting intervention, including frequency, timing, and content of the text messages.

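### Exploratory Aim 3: 8-week NRT adherence is to be tested as a mediator of Week 8 abstinence with no time order, so the result can be biased in either direction even if NRT has no effect.

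*Combined protocol and SAP*

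**What the plan says.** Hypothesis 3.1 (Specific Aims) predicts that "those who are adherent with the NRT regimen throughout the intervention, will have higher rates of cessation". Section A5 lists medication adherence as both moderator and mediator. In Section C2, under Use of Pharmacotherapies, the plan states: "After calculating a percentage of medications taken, medication adherence will be assessed as a mediator of treatment outcomes". Section C3 gives mediators part of one sentence: logistic regression on abstinence. It states no mediator window, lag or adjustment for earlier smoking status.

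On what the percentage is a percentage of, Section A2 says "I will evaluate an 8-week dual NRT regimen". The NRT paragraph of Section C2 then says "the lozenge is used ad libitum and provides acute nicotine administration" and that "participants will be given the opportunity to use the medications individually or together (participant choice, including none at all". Refills follow a contact at which participants are "asked how much NRT they used and if they would like to receive the next 2-week dose". For the control arm, "Those in the SC condition will receive standard counseling but no medications".

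On timing, "all participants will be encouraged to set a quit date", but no common quit day is fixed.

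Time-ordered data are planned. All participants are asked for total and daily patch and lozenge use at each contact, abstinence is asked at the 2-week check-ins, and Timeline Followback records daily smoking. The medication-use texts are described for MTI only.

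**The concern.** A mediator has to come before the outcome it is meant to explain. Here the exposure window ends with the outcome week and includes all the time after a relapse. Someone who relapses and stops NRT gets a low adherence score because of the relapse. Someone who has quit and feels no further need of NRT gets a low score because of the success. Either way, part of the adherence score is a consequence of smoking status, and the regression cannot separate that part from an effect of NRT.

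The pilot is meant to guide later work, and Section C2 hopes to separate NRT from texting in future grants. A biased adherence coefficient, in whichever direction, would misinform that step.

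The undefined percentage is a separate gap. It leaves the mediator without a value in one arm and without a scale for one product.

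**Working it through.** **1. The plan's own figures.** The plan gives no figure for the mediator analysis. Its only computed figures are in Table 2. Exact (Clopper-Pearson) intervals with n = 40 reproduce them: 20/40 gives 0.338 to 0.662, 12/40 gives 0.166 to 0.465, and 4/40 gives 0.028 to 0.237. This confirms only the basis of 40 per arm used below.

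**2. Windows.** Mediator: weeks 0 to 8. Outcome: self-report of the last 7 days at the end of Week 8. The outcome week lies inside the mediator window.

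**3. Denominator.** A person who uses the first 2-week supply and declines the rest scores 2/2 weeks = 100% of what was supplied, or 2/8 weeks = 25% of the regimen. In SC, the percentage of study supply is 0/0. For an ad libitum lozenge no planned amount is stated.

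**4. Null simulation, relapsers stopping.** All behaviour is assumed, because the documents give none. Relapse probability is 0.16 a week, independent of NRT use, and each MTI participant's mean daily use is drawn from beta(3,2). The model within MTI is logit P(abstinent) = a + b × (percentage of the 56 days with use ÷ 10), and OR = exp(b). The true OR is 1.
- A: all quit at the start, no re-quitting (0.84^8 = 25% abstinent at Week 8).
- B: half quit at the start, 3% a week re-quit, and those not yet quit keep using NRT (20% abstinent).
- C: as B, but those not yet quit use half as much NRT.

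| Relapsers who stop NRT | A | B | C |
|---|---|---|---|
| 0% | 1.01 | 1.00 | 1.25 |
| 25% | 1.16 | 1.06 | 1.34 |
| 50% | 1.32 | 1.12 | 1.44 |
| 100% | 2.03 | 1.23 | 1.99 |

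**5. Null simulation, successful quitters also stopping.** People smoke-free for at least 14 days stop NRT at 10/20/30% a week. With 50% of relapsers stopping, the OR is 1.13/1.02/0.93 (A), 1.00/0.91/0.84 (B) and 1.25/1.12/1.04 (C). With no relapser stopping and 20% a week of quitters stopping, it is 0.68/0.76/0.96 (A/B/C) if they resume NRT on relapse, and about 0.8 in A and B if they stay off. The sign is therefore not determined.

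**6. Do the obvious repairs help?** With 50% of relapsers stopping and no quitters stopping (A/B/C):
- 3-month outcome on 8-week use: 1.25/1.05/1.17.
- Week 8 outcome on early use alone: 1.10/1.02/1.19 (weeks 0-2) and 1.19/1.05/1.27 (weeks 0-4).
- Early use with abstinence at the closing check-in in the model: 0.99 to 1.01 in every scenario, both windows, both outcomes.

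**7. At the trial's size.** 800 two-arm trials of 40 per arm, Firth regression with arm in the model, 50% of relapsers stopping. For 8-week use the median OR is 1.31/1.12/1.44, with p<0.05 in 39%/6%/48%. For early use given check-in abstinence the median is 0.99 to 1.00, with p<0.05 in 2 to 4%. The standard error of that log OR is 0.17 to 0.21, so the 95% CI multiplies and divides the estimate by exp(1.96 × 0.17) = 1.40 to exp(1.96 × 0.21) = 1.51.

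**8. Does the denominator drive the bias?** A second null model used different assumptions: 30% abstinent, half of the others never quitting, and half of those who relapse or never quit stopping NRT 3 days later. The 8-week percentage was significant in 72.5% of trials with the full course as denominator and in 68.2% with supply as denominator. A block-by-block analysis among those still abstinent gave 6.0%. The missing time order produces the error, not the missing denominator.

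**The case against.** **The aim is exploratory and Section C3 puts estimation above significance.** True, and this keeps the point minor. But the estimate itself is biased, so setting p-values aside does not remove the problem.

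**Section C3 is brief rather than wrong.** It does not rule out lagged models or use of the check-in data, and the 8-week window is inferred from Hypothesis 3.1. That stands: the gap is an omission, and one should not say that the plan refuses to use those data.

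**Much of the measure is already defined.** The pharmacotherapy section records use per product and separates study product from purchased product, and the 8-week regimen is the natural reading for the patch. That also stands. Only the lozenge and SC remain open.

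**A reader might infer that the plan would falsely credit quitting to NRT.** The documents do not support that direction. It needs relapsers to stop NRT, or those still smoking to use less, more than successful quitters stop. Refills and use are the participant's choice, and neither rate is given. Under B, moreover, only 6% of trials reached p<0.05.

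**The table in the working shows associations within MTI, not indirect effects.** Correct. The simulated two-arm indirect effect was too unstable across SC use distributions and reference arms to serve as a headline. The two-arm adherence coefficients in step 7 show the same bias.

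**Conclusion.** The point holds as a minor one, confined to exploratory Aim 3. As written, the adherence coefficient and any indirect effect built on it cannot be read as mediation, because smoking status can change NRT use within the same window. With no NRT effect, the simulated OR per 10 points of use ran from 0.68 to 2.03. It is close to 1 where smoking status does not alter use, or where the two kinds of stopping roughly cancel. These figures are illustrations under assumed behaviour, not predictions for this trial. Neither the 3-month outcome nor an early window without earlier smoking status removes the problem.

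The undefined percentage for the lozenge and SC is a separate definitional gap. It is tempting to read it as the cause of the bias, but step 8 shows that it is not. Estimation of the abstinence rates and their difference under Aims 1 and 2 does not use the mediator and is unaffected.

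**What to change.** 1. **8-week percentage.** Report it per product within MTI only: for patch, with all four 2-week supplies as denominator; for lozenge, as the amount used. Call it a descriptive association, not mediation.

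2. **Time-ordered exploratory analysis, both arms.** Take the amount of patch and, separately, of lozenge used from any source in weeks 0-2. Repeat for weeks 0-4, since the first supply may be mailed up to a week after randomization. Report the arm difference in early use. Regress later abstinence on arm, early use and abstinence at the check-in that closes the window, by penalized (Firth) logistic regression. Ordinary logistic regression has no finite estimate if nobody smoking at that check-in is abstinent later. Add baseline FTND and motivation if events allow: 20 to 25% of 80 is only 16 to 20 events. Give 95% CIs and the number lacking the closing check-in.

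3. **Label.** Call this the association of early use with later abstinence given early smoking status, not a full indirect effect.

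The cost is analysis wording only, because the items are already planned in both arms. The downsides are real. Later use is ignored. Conditioning on early abstinence removes any NRT effect that acts through early quitting. Shared motivation can leave bias (simulated OR 1.11 to 1.12 if not adjusted for, 1.00 if measured perfectly). Precision is poor: if NRT use halved the daily relapse risk, the simulated true OR is only 1.05 to 1.07. With ln(1.05)/0.21 = 0.23 and ln(1.07)/0.17 = 0.40 standard errors, power is about 6 to 7%. The result can only be descriptive.
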